10.4 Secondary Objectives

The secondary objectives of this trial are to describe toxicity and, to obtain additional measures of efficacy including response rate and overall survival.

10.4.1 Toxicity

Patients will be evaluable for toxicity from the time of their first treatment with ficlatuzumab. The proportion of AEs will be reported in accordance with NCI CTCAE v.4.0 grading criteria.

10.4.2 Other Efficacy Endpoints

Response rate will be assessed by modified RECIST criteria, version 1.1. Overall survival will be measured from the date of randomization until the date of death.

10.5 Exploratory Objectives

The exploratory objectives of this trial are to describe patient reported quality of life and to evaluate whether candidate biomarkers are prognostic in the context of treatment with ficialtyzumab.

10.5.1 Patient-Reported Outcomes

Quality of life will be described according to FACT-H&N Symptom Index scores obtained at baseline and after two cycles of study treatment.

10.5.2 Biomarker endpoints

We will evaluate the relationship between clinical outcomes (PFS, RR) and candidate tumoral, genomic, peripheral, and immune biomarkers, potentially including but not limited to: tumor HGF and cMet expression; mutations in *PIK3CA*, *PTEN*, and *HRAS*; peripheral serum biomarkers including HGF, soluble HGF, and IL6; peripheral lymphocyte populations; archived and baseline immune infiltrate.

Two candidate mechanistic biomarkers will be prioritized for specialized alpha spending: 1) baseline HGF expression; 2) baseline cMet expression. Testing two biomarkers each at $\alpha = .05$ guarantees a maximum 10% false discovery rate for this exploratory objective.

Other candidate biomarkers in tumor and blood described above will be quantitatively measured and will be evaluated as predictors of PFS and/or tumor response in appropriate generalized linear models. Calculated p values for testing the significance of the prediction models will be adjusted for false discovery by the method of Benjamini and Hochberg.⁵¹

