1.8 Correlative Studies Background

1.8.1 Tumoral Activation of HGF/cMet Pathway

We have published a report of a cohort of 56 HNSCC patients with tumor protein levels of HGF and cMet calculated by the H score (intensity weighted by percent tumor).¹⁸ We found that HNSCC tumors overexpress both HGF and c-Met as compared to adjacent tissue, as demonstrated below in Figure 1. Ongoing work indicates a bidirectional positive feedback loop between tumor-associated fibroblasts (TAF) which secrete HGF, and HNSCC tumor cells whose conditioned media stimulate HGF secretion from TAFs.³⁴ In a preclinical HNSCC-TAF co-culture model, ficlatuzumab inhibited HNSCC progression via reduced cMet and mitogen-activated protein kinase (MAPK) signaling.³⁵

During the phase Ib trial evaluating the combination of ficlatuzumab and cetuximab in patients with cetuximab-resistant, recurrent and/or metastatic HNSCC, we evaluated three candidate baseline biomarkers for feasibility and relationship to response: VeriStrat; tumoral expression of pMet; and tumoral expression of HGF/cMet dimers. There was no relationship between VeriStrat status and PFS. pMet and HGF/cMet dimer analyses are pending.

[figure not shown]

Figure 1: HGF and c-Met are overexpressed in head and neck cancer. HGF and c-Met protein levels were assessed by immunohistochemistry in HNSCC tumors and paired adjacent mucosa (n = 26). Intensity (integer scale 0 to +3) and percent of tumor stained were evaluated. A weighted score of intensity times percent of tumor stained was calculated. A, tumor tissues showed increased HGF and c-Met staining compared with paired adjacent mucosal tissues. B, two-tailed Wilcoxon signed-rank test for paired samples indicated significant differences in weighted HGF and c-Met intensity in tumor versus paired adjacent mucosa (HGF; P < 0.001; c-Met; P = 0.04). C, HGF and c-Met immunohistochemistry score frequency distributions indicate that higher levels of HGF are more frequently present in HNSCC tumors than c-Met.¹⁸

In this clinical trial, patients will undergo a research biopsy at baseline. We will investigate the relationship between candidate biomarkers and clinical outcomes on each arm, including the following:

- Dimers (Monogram assay): HGF/cMet, EGFR/EGFR, EGFR/HER2
- Signaling proteins: pMet, bFGF, pMAPK, pAkt

We will also analyze HGF and cMet in archived diagnostic biopsies which took place before clinical cetuximab exposure, as available.

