2.3 Exploratory

- To describe patient-reported quality of life.
- To evaluate the relationship between clinical outcomes (Progression-Free Survival and Response Rate) and candidate tumoral, genomic, peripheral, and immune biomarkers, potentially including but not limited to:
 - Tumor HGF and cMet expression
 - mutations in PIK3CA, PTEN, and HRAS;
 - o peripheral serum biomarkers including HGF, soluble HGF, and IL6;
 - peripheral lymphocyte populations;
 - o archived and baseline immune infiltrate;
 - tumor HPV status.

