10.6 Statistical Analysis Plan

Progression-free and overall survival will be estimated for each arm using a Kaplan-Meier curve. Toxicities and the response rate will be tabulated and reported with 95% exact confidence intervals. The relationship between progression-free survival and the candidate biomarkers will be assessed using Cox proportional hazards models. The relationship with clinical response will be assessed using logistic regression models.

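### The 10% false discovery guarantee for HGF and cMet holds only with one test per marker, and the plan relates each marker to two outcomes without naming the protected one

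*Combined protocol and SAP*

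**What the plan says.** Section 10.5.2 singles out two markers for their own alpha, "1) baseline HGF expression; 2) baseline cMet expression". Each is tested at 0.05, and the section states that this "guarantees a maximum 10% false discovery rate for this exploratory objective".

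The outcomes come from three places:

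- **Section 10.5.2** opens with "We will evaluate the relationship between clinical outcomes (PFS, RR) and candidate tumoral" and other biomarkers. Tumor HGF and cMet expression come first in the list that follows.
- **Section 2.3**, the objective itself, speaks of the "relationship between clinical outcomes (Progression-Free Survival and Response Rate) and candidate tumoral" and other biomarkers, and again lists tumor HGF and cMet expression first.
- **Section 10.6** gives each outcome its own model: "The relationship between progression-free survival and the candidate biomarkers will be assessed using Cox proportional hazards models", and logistic regression for clinical response.

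The Benjamini-Hochberg adjustment in section 10.5.2 is stated only for the remaining candidate biomarkers, not for these two. Section 1.8.1, in the correlative background, also says the trial will investigate the "relationship between candidate biomarkers and clinical outcomes on each arm".

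**The concern.** The 10% limit depends on the number of tests, and the plan never fixes that number for the two prioritised markers. Both outcomes are in scope for them, each outcome has its own model, and no sentence chooses one outcome or shares the 0.05 between the two. An analyst following the text could test HGF against PFS and against response, do the same for cMet, report whichever result falls below 0.05, and cite 10% protection.

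These are the two markers that the plan chose to protect, so a positive finding for either would carry more weight than one from the wider exploratory set. It would be reported with an error guarantee that the described analysis does not have.

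**Working it through.** **Inputs.** Two prioritised markers, each tested at 0.05, with a stated maximum of 10% (section 10.5.2). Two outcomes, PFS and response (sections 2.3 and 10.5.2), with separate models (section 10.6). The correlations below are assumptions, because the documents give none.

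**Which quantity to compute.** The false discovery rate (FDR) is the expected share of false findings among all findings. It never exceeds the chance of at least one false finding, and it equals that chance when no association is real. A stated maximum must cover that case, so the calculation is made there.

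**Step 1: the plan's own figure, two tests.**

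- Union bound: 2 × 0.05 = 0.10. This reproduces the stated 10%.
- Independent tests: 1 − 0.95² = 0.0975.

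**Step 2: four tests (2 markers × 2 outcomes), each at 0.05.**

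- Union bound: 4 × 0.05 = 0.20.
- Independent tests: 1 − 0.95⁴ = 0.1855.

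**Step 3: allowance for correlation.** PFS and response are measured in the same patients, so their tests are likely to be correlated. Take two-sided tests with jointly normal statistics, and let the two markers be independent of each other. If p is the chance of at least one false finding for one marker across its two outcomes, the overall rate is 1 − (1 − p)². At a correlation of 0.9, p is 0.0704, so the rate is 1 − 0.9296² = 0.136.

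| Correlation between the outcome tests | Rate with four tests |
|---|---|
| 0 | 18.5% |
| 0.5 | about 17% |
| 0.7 | about 16% |
| 0.9 | 13.6% |
| 0.99 | 11.0% |

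When the two markers are also allowed to correlate at 0.5, with 0.9 between outcomes, the simulated rate is 12.6%. That is the lowest value over the grid tried (0 to 0.9 between outcomes, 0 to 0.5 between markers).

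**Step 4: per-test level that would keep 10% with four tests.** 0.10 / 4 = 0.025.

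**Step 5: conditional case only.** If these two markers were also tested separately in each of the two arms, there would be eight tests. Independence gives 1 − 0.95⁸ = 0.337. With 0.9 between outcomes and independent arms, the rate is 1 − (1 − 0.136)² = 0.25. The union bound is 8 × 0.05 = 0.40.

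**The case against.** The strongest reply is that the plan allots alpha per biomarker, not per marker-outcome pair, so one decision per marker was meant. On that reading 10% is correct, and the arithmetic is indeed not in error. The mention of PFS and response in section 10.5.2 introduces all candidates together, and the later sentence on predicting either outcome covers only the remaining markers. This reading is possible. But nothing says which outcome the single decision uses, and sections 2.3 and 10.6 put both outcomes in scope for the candidate biomarkers as a whole. A guarantee cannot rest on a choice that the plan does not make.

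A second reply is that the four-test figures assume every test has true size 0.05. With few responders, a logistic Wald test can be conservative. A simulation with 33 patients, assumed response rates of 5% to 17%, a normally distributed marker and no association gave a Wald size of 0.004 to 0.026, and a likelihood-ratio size of about 0.06. If the response tests had size 0.004 and everything were independent, the four-test rate would be 1 − 0.95² × 0.996² = 0.105. So the actual excess could be small with one choice of test. The plan names no test, and incidental conservatism is not a guarantee.

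A third reply is that the objective is exploratory. That is true, and it limits the consequence. Advancement to phase III (section 10.3) and futility stopping (section 10.7) rest on progression outcomes, not on biomarkers. It does not make the stated error property correct.

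In the other direction, a reader might infer from section 1.8.1 that eight tests are planned and that the rate is 34%. The documents do not support that as a planned analysis of these two markers. The sentence stands in the background, and its list names receptor dimers and signaling proteins, not HGF or cMet expression. The list is open-ended, so the two markers are not excluded. However, section 10.6 says per arm only for the Kaplan-Meier estimates, and section 10.5 frames the question as prognosis under ficlatuzumab, which both arms receive.

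**Conclusion.** The point stands as a mismatch between a stated error property and the analysis described, not as an arithmetic slip. The 10% maximum is right for one test per marker, and the plan does not limit the tests to that. With both outcomes tested at 0.05, the rate under no association is 18.5% for independent tests, about 14% at an assumed outcome correlation of 0.9, and at most 20% under any dependence. The 18.5% is an independence value, not a ceiling. All these figures assume tests of true size 0.05 and no real association, which is the case that a maximum must cover. If some associations are real, the FDR is lower. By-arm testing of these markers would raise the rate to about 25% to 34%, but section 10 does not state such testing, and the conclusion does not need it.

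**What to change.** Any one of these changes to section 10.5.2 is enough:

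1. **Name one protected test per marker at 0.05**, for example PFS in a Cox model stratified by arm with both arms included. Move response and any by-arm results for HGF and cMet into the Benjamini-Hochberg set. The 10% statement is then true as it stands.
2. **Control all HGF and cMet tests together**, by Benjamini-Hochberg at 10% or, for four tests, at 0.025 each. The 0.025 level holds under any dependence, while the Benjamini-Hochberg limit needs independent or positively dependent tests.
3. **Delete the guarantee** and report the results as unadjusted and exploratory.

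The choice among them is the sponsor's. The first keeps full alpha for one question per marker, and the second keeps both outcomes at a lower level. The cost is a change of wording, with no effect on sample size or conduct. Some exploratory results would lose nominal significance.

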10.6 Statistical Analysis Plan

Progression-free and overall survival will be estimated for each arm using a Kaplan-Meier curve. Toxicities and the response rate will be tabulated and reported with 95% exact confidence intervals. The relationship between progression-free survival and the candidate biomarkers will be assessed using Cox proportional hazards models. The relationship with clinical response will be assessed using logistic regression models.

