1.4 Phase Ib Study of the Combination of Ficlatuzumab and Cetuximab

We recently completed a phase Ib study of the combination of ficlatuzumab and cetuximab in patients with cetuximab-resistant, recurrent and/or metastatic HNSCC (NCT 02277197; Bauman JE et al, ASCO 2017). In this Narayana k-in-a-row phase I design, fixed-dose cetuximab was administered at 500 mg/m² IV every 2 weeks. Ficlatuzumab dose tiers were 10 mg/kg (starting

dose) or 20 mg/kg IV every 2 weeks (tier 2), with inter-patient escalation or de-escalation based on cumulative dose-limiting toxicities (DLT). The RP2D was set at dose tier 2 if no DLTs were observed after 8 enrolled patients, with expansion planned to n=12. Key eligibility criteria included: R/M HNSCC, cetuximab resistance (recurrence within 6 months of cetuximab-radiation or progression during/within 6 months of palliative cetuximab); ECOG performance status 0-1; mandatory baseline research biopsy. Candidate biomarkers included serum VeriStrat classification and tumor expression of pMet and HGF/cMet dimers.

From Sept 2015-June 2016, 12 pts were enrolled and treated. Primary site: 1 oral cavity; 3 oropharynx (1 p16+); 2 hypopharynx; 5 larynx; 1 external auditory canal. Platinum-refractory: 11/12. VeriStrat: 8 poor; 4 good. Three were treated at tier 1 and 9 at tier 2. No DLTs were observed. Grade 3 adverse events included: edema (1), hypoalbuminemia (1), infection (2), and thromboembolic event (2). Median PFS and OS at RP2D were 6.0 mos (90% CI = 2 mos – not reached) and 8.2 mos (90% CI = 2.7 mos – not reached), respectively. Response rate was 17% (90% CI = 0-28%): 2/12 partial response (PR); 1/3 at 10 mg/kg; 1/9 at 20mg/kg. Clinical benefit rate (PR + stable disease) was 67%. VeriStrat was not associated with PFS.

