1.8.3 Genomic Alterations: PIK3CA, PTEN, and HRAS

The mutational landscape of HNSCC was assessed by whole exome sequencing of 74 tumor-normal pairs.³⁷ Several mutations in HNSCC interact with the EGFR and HGF/c-Met signaling pathways and may modulate the impact of pathway antagonism. These include *PIK3CA* (8%), *PTEN* (8%), and *HRAS* (4%) mutations. As we did not confirm the presence of activating *MET* mutations or amplification described by others, and the TCGA has demonstrated less than 1% prevalence in >300 case of *MET* mutation or *MET* amplification, we will not assess *MET* mutation or amplification status.¹⁹.³⁸

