10.3 Sample Size Determination

The primary objective of this study is to estimate PFS in both arms. The sample size calculation thus is based on the primary endpoint of PFS. Given no data are available for single-agent ficlatuzumab in patients with recurrent and/or metastatic HNSCC refractory to platinum, cetuximab, and PD-1 inhibition, the historical control will be represented by dealer's choice chemotherapy in the phase III trial of nivolumab in platinum-refractory HNSCC: 2 months. This median PFS is very similar to single-agent data in the refractory, recurrent and/or metastatic setting for cetuximab, afatinib, and methotrexate ^{49, 50}. We would like to investigate whether the new regimen in either arm can improve the median PFS from 2 months to 3.33 months (i.e. 60% improvement in median PFS). To detect such an improvement, the study design requires 66 eligible patients (33 eligible patients on each arm) over 24 months with an additional follow-up of 6 months (making the study duration of approximately 2.5 years in total), using a log-rank test with 90% power while assuming a 0.10 one-sided type 1 error rate. Full information for the primary endpoint of PFS will occur at 33 events per arm. To account for an assumed 10% ineligibility/drop-out rate, 74 patients in total will be accrued to obtain the necessary 66 eligible randomized patients. If one arm achieves the hypothesized median PFS, that arm will be advanced to phase III testing. If both arms achieve the hypothesized PFS, the numerically superior arm will be advanced to phase III testing.

Definition of Evaluable:

Subjects who receive at least one dose of ficlatuzumab will be considered evaluable.

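### Section 10.6 plans ordinary logistic regression of response on rare mutations, with no sparse-data method or test named, although an empty cell is the usual result for a single arm

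*Combined protocol and SAP*

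**What the plan says.** Section 10.6 relates PFS to the biomarkers by Cox models. For response it says: "The relationship with clinical response will be assessed using logistic regression models". The same paragraph specifies exact 95% intervals for the response rate and toxicities, but nothing comparable for the biomarker models.

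Section 10.5.2 sets aside HGF and cMet expression as the two prioritized markers. The other markers "will be evaluated as predictors of PFS and/or tumor response in appropriate generalized linear models", and their p-values go into a Benjamini-Hochberg adjustment. Section 2.3 lists "mutations in PIK3CA, PTEN, and HRAS" among the candidates, and section 1.8.3 gives their frequency: "These include *PIK3CA* (8%), *PTEN* (8%), and *HRAS* (4%) mutations".

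The documents do not say whether the mutation models are fitted within each arm or with the arms pooled. Section 1.8.1 says "We will investigate the relationship between candidate biomarkers and clinical outcomes on each arm", but the list after that sentence consists of receptor dimers and signaling proteins. No test statistic, penalized or exact method, or minimum carrier count is stated.

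**The concern.** With few responders and few carriers, a mutation-by-response table often has no patient in one cell. Maximum likelihood then has no finite odds ratio. Software reports a very large coefficient with a very large standard error and a Wald p-value close to 1, even when every carrier responded. If that default output is used, a mutation that marks responders is likely to be missed, and the artificial p-value enters the Benjamini-Hochberg family. The main cost is lost signal and missing estimates, not extra false positives.

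Leaving the test unnamed also means that one table can be reported as null or as significant depending on which p-value is read from the output.

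**Working it through.** **No figure to reproduce.** The plan gives no responder count, cell count or power for these models. The denominator is consistent: 2 x 33 = 66, and 66 / 0.90 = 73.3, rounded up to the 74 to be accrued.

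**Inputs**
- Patients: 33 per arm, 66 pooled (section 10.3).
- Carrier frequency p: 0.08 for PIK3CA and PTEN, 0.04 for HRAS (section 1.8.3).
- Response rate r: section 1.4 reports "2/12 partial response (PR); 1/3 at 10 mg/kg; 1/9 at 20mg/kg", so 1/9 = 0.11 at the dose used here and 2/12 = 0.17 overall. This is an assumption for both arms. The documents give no HNSCC response rate for ficlatuzumab alone.

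**Expected counts per arm**
- Responders: 33 x 1/9 = 3.7 to 33 x 2/12 = 5.5.
- Carriers: 33 x 0.08 = 2.6 and 33 x 0.04 = 1.3.
- Carriers who respond: 33 x 0.04 x 1/9 = 0.15 to 33 x 0.08 x 1/6 = 0.44.

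**Probability of an empty cell, no association.** Cell probabilities are pr, (1-p)r, p(1-r) and (1-p)(1-r). The chance that at least one cell is empty follows by inclusion-exclusion on terms of the form (1 - cell probability)^n. For n = 33, p = 0.08, r = 1/6:
- no responding carrier: (1 - 0.0133)^33 = 0.642
- no non-responding carrier: (1 - 0.0667)^33 = 0.103
- no responding non-carrier: (1 - 0.1533)^33 = 0.004
- less the overlaps, mainly no carrier at all, 0.92^33 = 0.064, and no responder at all, (5/6)^33 = 0.002
- total: about 0.68

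| Analysis | Marker | r = 0.17 | r = 0.11 |
|---|---|---|---|
| Single arm, n = 33 | PIK3CA or PTEN (8%) | 68% | 78% |
| Single arm, n = 33 | HRAS (4%) | 87% | 91% |
| Pooled, n = 66 | PIK3CA or PTEN (8%) | 42% | 56% |
| Pooled, n = 66 | HRAS (4%) | 68% | 77% |

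In a single arm, 61-69% of datasets have separation (odds ratio zero or infinite). The rest of each total is an arm with no carrier or no responder, where the odds ratio is undefined. An arm has no carrier in about 6% (0.92^33) or 26% (0.96^33) of cases.

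With a true odds ratio of 3 to 10, the single-arm figures are 47-60% for PIK3CA or PTEN and 77-83% for HRAS.

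**What each test makes of an empty cell**
- Carriers 2 of 2 responding, non-carriers 4 of 31. Log-likelihood with the marker: 4 ln(4/31) + 27 ln(27/31) = -11.92. Without it: 6 ln(6/33) + 27 ln(27/33) = -15.65. The likelihood-ratio statistic is 7.45, p = 0.006. Fisher p = 0.028; Wald p = 0.999.
- Carriers 0 of 3, non-carriers 6 of 30: likelihood-ratio p = 0.26, Fisher p = 1.00, Wald p = 0.999.

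**Detection of a response-enriching marker.** Assumed, not from the documents: 8% prevalence, response 15% in non-carriers and 70% in carriers, two-sided 0.05 before any multiplicity adjustment. Tables were enumerated exactly. A Wald test with an empty cell counts as not significant, and the pooled rows omit an arm term.

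| | Wald | Ordinary likelihood ratio | Firth likelihood ratio | Fisher |
|---|---|---|---|---|
| n = 33 | 16% | 51% | 47% | 34% |
| n = 66 | 55% | 74% | 76% | 70% |

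With no association, both likelihood-ratio tests reject in about 2-4% of datasets across the settings in the first table.

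**The case against.** The strongest reply is that the plan never specifies Wald tests. Section 10.6 names only a model, and section 10.5.2 speaks of testing the significance of the prediction models, which reads naturally as a likelihood-ratio test and allows whatever generalized linear model is appropriate. This stands in part. A reader might infer that the planned regression yields no usable p-value at all. The documents do not support that: an ordinary likelihood-ratio test gives a finite p-value whenever there is at least one carrier and one responder, and it performs about as well as Firth. It does not repair the odds ratio, which stays zero or infinite whichever p-value is used.

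A reader might also infer that a better method would reveal a mutation that abolishes response, the resistance pattern of most biological interest. It would not. With 0% response in carriers and 11% or 17% in non-carriers, Firth and Fisher detect the effect in at most about 0.1% of datasets, even pooled. For 0 of 5 carriers against 11 of 61 non-carriers, the likelihood-ratio p-value is 0.17 and Fisher's is 0.58. The limit there is information, not the estimator.

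Third, a reader might take the per-arm wording in section 1.8.1 as covering the mutations. It introduces protein markers, so the per-arm reading is an inference. If the arms are pooled, an empty cell is still the more likely result for HRAS, but PIK3CA and PTEN fall to about half.

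Finally, the objective is exploratory, the list is only of potential markers, and PFS is also analysed by Cox models. All true, and the reason that this is a small point.

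**Conclusion.** The point holds in a limited form. For the three mutation markers, ordinary logistic regression gives no finite odds ratio in 68-91% of single-arm and 42-77% of pooled analyses under no association, and the plan names neither a fallback nor a test. If Wald output is used, detection of the illustrative strong marker falls from about half to 16% in one arm, and from about three quarters to 55% pooled.

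This rests on the mutation frequencies in section 1.8.3, on full enrollment of 33 per arm, and on a response rate from 12 patients. A lower response rate in Arm A, or an arm stopped early under section 10.7 (from 8 patients; expected size 21.3 under the null), would leave still sparser tables. The point does not extend to HGF and cMet expression analysed as continuous scores, where chance complete separation with 4-6 responders among 33 is below 0.01%. It does not touch the primary analysis.

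**What to change.** Add to section 10.6, for the binary mutation markers:
- Fit Firth-penalized logistic regression and report the odds ratio with a profile-likelihood interval and a penalized likelihood-ratio p-value. If the ordinary model is kept, use likelihood-ratio or exact p-values, not Wald.
- Carry those p-values into the Benjamini-Hochberg adjustment of section 10.5.2.
- State whether the arms are pooled. One pooled fit per marker with arm as a covariate, and per-arm results as description, makes best use of the few carriers.
- Where there are no carriers or no responders, report counts only. Say that the sample cannot show a mutation that abolishes response.

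The cost is a few lines of text and standard software, with no extra data. Section 5.1 ends dosing by March 31, 2021, so responses may already be known. The amendment should record whether the mutation-by-response tables had been seen when the method was chosen.
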